12.2.2 Analysis Plan

The phase 1B portion of this trial is designed to allow preliminary assessments of safety and biological activity. No pre-specified hypothesis testing will be performed.

The phase 2 portion of this trial will be powered to detect an improvement in response equal to the combined overall response rate (ORR) of each intervention alone (SD-101 and ibrutinib).

12.3 Sample Size

12.3.1 Accrual estimates

Sample Size – Dose Escalation Cohorts

6 to 15 subjects may be enrolled in the dose de-escalation cohorts in a 6+3 study design.

Sample Size – Phase 2 Expanded Cohort

15 subjects will be enrolled in the phase 2 expanded cohort.

We estimate accruing an average of 10 subjects per year based on prior experience with this subject population. The Stanford STRIDE database reports 40 subjects with BOTH an ICD9 diagnosis of nodular lymphoma (202.0) AND encounter for antineoplastic chemotherapy and immunotherapy (V58.1) occurring in the year 2015 – indicating the number of subjects with this diagnosis who required treatment in the prior calendar year.

12.3.2 Sample size justification

The reported overall response rate with single-agent ibrutinib in a similar population of relapsed/refractory low-grade follicular lymphoma has been 30% (12 of 40 subjects) (12), and

we previously reported an ORR of 27% to intratumoral CpG (4 of 15 subjects) (50). We will therefore expect overall response rate of >57% (ie, a 27% improvement over ibrutinib alone).

This trial design will enroll a minimum of 21 subjects at the recommended phase 2 dose (a minimum of 6 subjects in phase 1b and 15 subjects in the phase 2 expansion). For a true response rate of 57%, this sample size will provide 83.6% power to detect a significantly improved (95% confidence interval) response rate as compared to the previously reported ORR of 30% with ibrutinib alone.

A total of 6 to 15 subjects will be enrolled in the phase 1B 6 x 3 dose de-escalation portion. An additional 15 subjects will be enrolled in the expanded phase 2 cohort.

If $\leq 1/6$ subjects experience a DLT at a dose of intratumoral SD-101 of 3 mg, we will proceed to the expansion phase. If $2/6$ subjects experience a DLT at 3 mg, then an additional 3 subjects will be enrolled in the same dosing cohort. If ≥ 3 of 6 to 9 subjects experience a DLT, then a dose de-escalation cohort -1 of 6 subjects will be opened.

The sample size of 15 subjects in the expanded phase 2 cohort (with resulting total number of 21 to 24 subjects at the RP2D in the combined 1b/2 phases) allows estimation of the response rate $+\/- 0.21$ with 90% confidence. The chance of obtaining three or fewer responses out of 15 is only 2.1% if the true response rate is 49%, with 49% ORR being a historical benchmark for response rate in this population.

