SAMPLE SIZE	
This research study is looking for a total of up to 30 subjects with low-grade follicular lymphoma, marginal zone lymphoma, or mantle cell lymphoma. All subjects will be enrolled at Stanford University. A total of 6 to 15 subjects will be enrolled in the phase 1B 6 x 3 dose de-escalation portion. An additional 15 subjects will be enrolled in the expanded phase 2 cohort.
 
If ≤ 1 of 6 subjects experience a DLT at a dose of intratumoral SD-101 of 3 mg, we will proceed to the expansion phase. If 2 of 6 subjects experience a DLT at 3 mg, then an additional 3 subjects will be enrolled in the same dosing cohort. If ≥ 3 of 6 to 9 subjects

	experience a DLT, then a dose de-escalation cohort -1 of 6 subjects will be opened.
STATISTICAL CONSIDERATIONS	The sample size of 15 subjects in the expanded phase 2 cohort (with resulting total number of 21 to 24 subjects at the RP2D in the combined 1b/2 phases) allows estimation of the response rate +/- 0.21 with 90% confidence. The chance of obtaining three or fewer responses out of 15 is only 2.1% if the true response rate is 49%, with 49% ORR being a historical benchmark for response rate in this population.

SCHEMA

LIST OF ABBREVIATIONS AND DEFINITION OF TERMS

AE	Adverse event
BID	Twice daily
CBC	Complete blood count
CNS	Central nervous system
CpG	Cytosine-phosphate-Guanine
CRF	Case report/Record form
CR	Complete response
CTCAE	Common Terminology Criteria for Adverse Events
CTL	Cytotoxic T lymphocyte
DLT	Dose Limiting Toxicity
DSMB	Data Safety Monitoring Board
ECG	Electrocardiogram
GI	Gastrointestinal
Hgb	Hemoglobin
HIV	Human Immunodeficiency Virus
HPF	High-power field
HTN	Hypertension
IRB	Institutional Review Board
ISS	Immunostimulatory sequence
IV	Intravenous
LDH	Lactate dehydrogenase
LLN	Lower limit of normal
MTD	Maximum Tolerated Dose
ODN	Oligonucleotide
OS	Overall survival
PBL	Peripheral blood leukocytes
PLT	Platelet
PD	Progressive disease
PFS	Progression free survival
PQC	Product Quality Complaint
PR	Partial response
QD	Once daily
RECIST	Response evaluation criteria in solid tumors
RP2D	Recommended phase 2 dose
RR	Response rate
SAE	Serious adverse event
SD	Stable disease
SD-101	Immunostimulant CpG injection (Dynavax)
TTP	Time to progression
ULN	Upper limit of normal
UNK	Unknown
WBC	White blood cell
WHO	World Health Organization

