In the PCYC-1121-CA study of 63 patients with marginal zone lymphoma(13), ibrutinib was shown to be active, with an overall response rate of 48% with a median duration of response not reached. Response rates were similar across all marginal zone subtypes (MALT, nodal, splenic). On the basis of this trial, ibrutinib received accelerated approval for adult patients with marginal zone lymphoma after at least one prior anti-CD20-based therapy.

Efficacy of Ibrutinib in Mantle Cell Lymphoma

Ibrutinib is FDA-approved for the treatment of relapsed/refractory treatment of mantle cell lymphoma. This is based on an overall response rate of 65.8% with median duration of response of 17.5 months seen in the PCYC-1104-CA trial of 111 patients (14). Ibrutinib is now frequently used in the treatment of relapsed mantle cell lymphoma and is being study as a front-line therapy for MCL.

Dosing rationale

Dosing of ibrutinib will be 560 mg daily, based on the proven safety at this level and efficacy in follicular lymphoma as discussed above. This is also the FDA-approved dose for treatment of mantle cell lymphoma and marginal zone lymphoma.

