3.1 Inclusion Criteria

- 3.1.1 Biopsy-confirmed Grade 1 or 2, or 3A follicular lymphoma; mantle cell lymphoma; or marginal zone lymphoma. Subjects must have relapsed from or are refractory to prior therapy.
- 3.1.2 Subjects must have at least one site of disease that is accessible for intratumoral injection of SD-101 (*diameter $\geq 10\text{mm}$*), percutaneously.
- 3.1.3 Subjects must have at least one site of measurable disease (see Section 10.2.2 for definition of measurable disease) other than the injection site which is not included in the radiation field.
- 3.1.4 ECOG Performance Status of 0 or 1
- 3.1.5 Subjects must be 18 years of age or older.
- 3.1.6 Required values for initial laboratory tests:
 - a) Absolute neutrophil count (ANC) $\geq 1000/\text{mm}^3$ independent of growth factor support
 - b) Platelets: $\geq 100,000/\text{mm}^3$ or $\geq 50,000/\text{mm}^3$ if bone marrow involvement independent of transfusion support in either situation
 - c) Hemoglobin: $\geq 8 \text{ g/dL}$ (may be transfused)

- d) Creatinine: Creatinine clearance > 25 mL/min
- e) AST/ALT: $\leq 3 \times$ ULN
- f) Bilirubin: $\leq 1.5 \times$ ULN (except for subjects with Gilbert's Syndrome or of non-hepatic origin)

3.1.7 Must be at least 4 weeks since treatment with standard or investigational chemotherapy, biochemotherapy, major surgery, radiation, cytokine therapy, and 8 weeks since any monoclonal antibodies or immunotherapy, and recovered from any clinically significant toxicity experienced during treatment.

3.1.8 Women of childbearing potential and men who are sexually active must be practicing a highly effective method of birth control during and after the study (see Appendix E) consistent with local regulations regarding the use of birth control methods for subjects participating in clinical trials. Men must agree to not donate sperm during and after the study. For females, these restrictions apply for 1 month after the last dose of study drug. For males, these restrictions apply for 3 months after the last dose of study drug.

3.1.9 Women of childbearing potential must have a negative serum (beta-human chorionic gonadotropin [β -hCG]) or urine pregnancy test at Screening. Women who are pregnant or breastfeeding are ineligible for this study.

3.1.10 Life expectancy greater than 4 months.

3.1.11 Able to comply with the treatment schedule.

3.1.12 Ability to understand and the willingness to sign a written informed consent document.

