12.2 Primary Analysis

12.2.1 Analysis Population

Phase 1B – Safety

The safety population will consist of all enrolled subjects who received at least one dose of any study treatment. The safety population will be used for the analysis of safety data.

Phase 2 – Efficacy

The response-evaluable population is defined as all enrolled subjects who received at least one dose of study treatment (ibrutinib or SD-101) and provided at least one post-baseline response (or disease) assessment. The response-evaluable population will be used as the primary population for analyses based on overall response.

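### The pooled phase 2 response rate is powered against 30%, a follicular-lymphoma-only rate for ibrutinib, although marginal zone and mantle cell lymphoma, with cited rates of 48% and 65.8%, are also eligible without a cap

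*Combined protocol and SAP*

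**What the plan says.** The powered comparison is in section 12.3.2. It takes 30% (12 of 40) as the single-agent ibrutinib response rate in relapsed or refractory low-grade FL and adds 27% (4 of 15) for intratumoral CpG, which gives a target of 57%. With at least 21 subjects at the recommended phase 2 dose, it claims 83.6% power to show a significantly improved "response rate as compared to the previously reported ORR of 30% with ibrutinib alone". The only indication of the significance rule is a parenthetical reference to a 95% confidence interval. Section 12.2.2 describes phase 2 as "powered to detect an improvement in response equal to the combined overall response rate (ORR) of each intervention alone". Section 12.3.3 repeats the same two rates and no others.

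The enrolled population is wider. Section 3.1.1 admits "Biopsy-confirmed Grade 1 or 2, or 3A follicular lymphoma; mantle cell lymphoma; or marginal zone lymphoma", and the synopsis describes a "total of up to 30 subjects with low-grade follicular lymphoma, marginal zone lymphoma, or mantle cell lymphoma". No quota by histology is given. Section 2.2.2 reports that in MZL "ibrutinib was shown to be active, with an overall response rate of 48% with a median duration of response not reached". Of the MCL approval it says: "This is based on an overall response rate of 65.8% with median duration of response of 17.5 months".

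Section 12.2.1 pools everyone who was treated and assessed: "The response-evaluable population will be used as the primary population for analyses based on overall response". No analysis by histology appears in sections 10.2 or 12.

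The synopsis and section 12.3.2 also give the probability of three or fewer responses in 15 at a true rate of 49%, "with 49% ORR being a historical benchmark for response rate in this population". No source is given for the 49%.

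**The concern.** In a single-arm trial the fixed reference rate is the only comparator, so it has to be the rate that ibrutinib alone would produce in the subjects actually enrolled. By the protocol's own figures, 30% is that rate only if every subject has FL. Each MZL or MCL subject raises the response rate expected from ibrutinib alone while the reference stays at 30%. The 57% target is itself below the 65.8% cited for ibrutinib alone in MCL.

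What is at stake is the reading of the primary efficacy result. A pooled ORR well above 30% would be read as evidence that SD-101 and radiation add to ibrutinib, when some or all of the excess could be case mix. The chance of that error depends on two things the documents do not give: the mix and the rejection rule. The 49% benchmark adds to the difficulty, because the same section then holds two reference rates 19 points apart without reconciling them.

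**Working it through.** **Inputs.** From 12.3.2: null 0.30, alternative 0.57, n = 21, stated power 83.6%. From 2.2.2 and 12.3.2: ibrutinib-alone rates of 0.30 (FL), 0.48 (MZL) and 0.658 (MCL). The documents give no histology mix, so the mixes below are assumptions.

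**1. Reproduce the plan's power.** One-sample normal approximation, one-sided 5%:

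Φ[(0.57 − 0.30 − 1.645·√(0.30·0.70/21)) / √(0.57·0.43/21)] = Φ[(0.27 − 0.1645)/0.1080] = 0.836.

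This matches 83.6%. The two-sided 5% version gives 75.3%, so the plan's figure is a one-sided 5% calculation.

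**2. Find the rejection rule.** The boundary in step 1 is 21·(0.30 + 1.645·0.10) = 9.75, i.e. at least 10 of 21. Two other rules are consistent with the words about a 95% interval:
- At least 11 of 21 is the first count with a Wald lower limit above 0.30 (0.310).
- At least 12 of 21 is the first count with a Clopper-Pearson lower limit above 0.30 (0.340; 11 of 21 gives 0.298).

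Exact power at 57% is 86.2%, 74.3% and 58.6% for 10, 11 and 12.

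**3. Compute the false-positive rate if the combination adds nothing to ibrutinib.** The number of responders is then the sum of three independent binomials with probabilities 0.30, 0.48 and 0.658 (a Poisson-binomial). The expected pooled rate is

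p0 = (0.30·nFL + 0.48·nMZL + 0.658·nMCL)/21.

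For example, 17/2/2 gives (5.10 + 0.96 + 1.316)/21 = 0.351. Exact upper tails:

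| FL/MZL/MCL | p0 | ≥10 | ≥11 | ≥12 |
|---|---|---|---|---|
| 21/0/0 | 0.300 | 6.8% | 2.6% | 0.9% |
| 18/2/1 | 0.334 | 12.2% | 5.3% | 2.0% |
| 17/2/2 | 0.351 | 15.8% | 7.3% | 2.9% |
| 15/4/2 | 0.368 | 20.3% | 10.0% | 4.2% |
| 11/5/5 | 0.428 | 40.3% | 24.1% | 12.3% |
| 7/7/7 | 0.479 | 60.1% | 42.1% | 25.6% |

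**4. Compute power against the weighted null.** Put p0 in place of 0.30 in the step 1 formula, with the true rate kept at 57%. The exact column uses the smallest count whose no-benefit tail is at most 5%.

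| FL/MZL/MCL | Plan formula, true 57% | Plan formula, true p0 + 0.27 | Exact 5% cut-off | Exact power, true 57% |
|---|---|---|---|---|
| 17/2/2 | 67% | 82% | ≥12 | 59% |
| 15/4/2 | 60% | 82% | ≥12 | 59% |
| 11/5/5 | 37% | 82% | ≥14 | 25% |
| 7/7/7 | 21% | 83% | ≥15 | 13% |

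At one-sided 2.5% the cut-offs are 13, 13, 14 and 15.

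**The case against.** The strongest reply is that the documents never set a phase 2 test. Section 12.2.2 gives no boundary, and the synopsis frames the sample size as estimation (±0.21 with 90% confidence) without mentioning 30%. The one numeric criterion for future work, at least 6 responses in section 12.4, is not tied to 30% either. On this view, at least 10 of 21 is a rule inferred from a power figure, and part of its excess over 5% comes from the normal approximation, since the all-FL rate is already 6.8%. If the 95% interval is taken as exact and two-sided, the rule is at least 12 of 21. The no-benefit pass rate is then 2.0% to 4.2% for the mixes with 3 to 6 non-FL subjects. The highest rates need about half or more non-FL subjects, and nothing supports equal thirds: the title refers to follicular lymphoma and the accrual estimate counts nodular lymphoma only. Finally, 30% is not settled even for FL, because section 2.2.2 also reports 7 of 13 with more than 50% shrinkage.

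Much of this stands as a limit on the size of the problem. It does not remove the mismatch. Section 12.3.2 claims power for a significantly improved rate over ibrutinib alone, which is a comparative claim however the test is written. The at-least-12 rule has 59% exact power at 57%, so the plan cannot rely on it and also keep 83.6%. A title and an accrual source do not cap enrolment. The 49% benchmark does not help either: it has no source or stated mix and serves only the three-of-15 calculation.

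**Conclusion.** The concern holds and should be fixed before the response rate is analysed. The 83.6% is arithmetically sound, but only for a sample made up entirely of FL, which nothing in the plan ensures. Once other histologies enrol, exceeding 30% is not in itself evidence of improvement over ibrutinib alone.

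The size depends on the mix and the rule. At the rule the plan's power implies, three non-FL subjects of 21 nearly double the false-positive rate (6.8% to 12.2%), and six triple it (20.3%). Rates of 40% to 60% need about half or more non-FL subjects. Under the exact-interval rule the rate stays below 5% up to six non-FL subjects and reaches 12.3% and 25.6% in the two most mixed cases.

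These figures assume n = 21 (the planned minimum), independent responses, and the cited ibrutinib rates taken as the true rates. Section 12.4's criterion of 6 responses is separate and is not affected.

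**What to change.** In section 12.2.2:

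1. Report ORR by histology with exact 95% confidence intervals, and limit the comparison with 30% to the FL subset.
2. For any pooled comparison, replace 30% with p0 = (0.30·nFL + 0.48·nMZL + 0.658·nMCL)/N from the enrolled counts. Use the exact Poisson-binomial tail at a stated one-sided alpha.
3. State that the historical rates are estimates (the exact 95% interval for 12 of 40 is 17% to 47%) and that sections 3.1 and 3.2 do not exclude prior ibrutinib. Add a sensitivity range for the reference rates.

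In section 12.3.2, restate the alternative (57% or p0 + 27 points) and the power against the new null, over a range of assumed mixes because the counts are unknown in advance. Give a source for the 49% and reconcile it with the null, or delete it.

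The cost is wording and a short exact calculation, with no new data or subjects. The downside is a higher bar. If the target stays at 57%, plan-formula power against p0 drops to between 67% (17/2/2) and 21% (7/7/7). It stays at 82–83% only if the target moves to p0 + 27 points, and that assumes the CpG gain seen in 15 low-grade lymphoma subjects carries over to MCL. The FL-only comparison also loses power. With 17, 15, 11 or 7 FL subjects the plan formula gives 77%, 72%, 61% and 47%. The exact one-sided 5% rules (at least 9, 9, 7 and 5 responses) give 72%, 52%, 45% and 36%.

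### Section 12.3.2 powers phase 2 against a 30% response rate but calls an unsourced 49% a historical benchmark, and nothing says which rate the single-arm result is judged against

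*Combined protocol and SAP*

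**What the plan says.** Two rates appear in section 12.3.2 of the combined protocol and SAP.

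- **30%.** The power paragraph assumes a minimum of 21 subjects at the recommended phase 2 dose and states: "For a true response rate of 57%, this sample size will provide 83.6% power". The gain is to be shown with a 95% confidence interval, and the comparator is given in these words: "as compared to the previously reported ORR of 30% with ibrutinib alone". The 30% is 12 of 40 subjects with relapsed or refractory follicular lymphoma. Section 12.3.3 (effect size) repeats it and does not mention 49%.
- **49%.** The last paragraph gives a 2.1% chance of three or fewer responses in 15 at a true rate of 49%, and describes that rate as follows: "with 49% ORR being a historical benchmark for response rate in this population". The statistical considerations row of the synopsis repeats this sentence and omits both the 30% and the power, so a reader of the synopsis sees only 49%.

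The 57% is the sum of 30% for ibrutinib and 27% (4 of 15) for intratumoral CpG. Section 3.1 admits follicular, mantle cell and marginal zone lymphoma. Section 2.2.2 gives ibrutinib-alone ORRs of 48% in marginal zone and 65.8% in mantle cell lymphoma.

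Sections 12.1 and 12.2.2 state no test, null rate or success threshold. The only numeric criterion, in section 12.4, is at least 6 responses, with no denominator; it concerns whether to redesign.

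**The concern.** Phase 2 has one arm, so the historical rate is the only comparator for its primary endpoint. The plan uses one rate to justify the sample size and attaches the word historical to another, 19 points higher (49 − 30). The expected 57% is a 27-point gain over the first and an 8-point gain over the second.

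If the benchmark is not fixed beforehand, it can be chosen once the responses are known, and a middling ORR can be reported either as an improvement or as no better than history. The reassuring 2.1% is also calculated at the higher rate, although the power is calculated at the lower one.

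**Working it through.** **Inputs.** From section 12.3.2: 30%, 49%, a true rate of 57%, n = 21 (range 21 to 24), and 15 subjects for the 2.1% statement. From section 2.2.2: 48% and 65.8%. The plan mentions a 95% confidence interval but gives neither the test nor its sidedness, so both one-sided 5% and two-sided 95% are shown.

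**1. The plan's own figures reproduce.**

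- Power against 30%, one-sided 5% normal approximation: Φ[(0.57 − 0.30 − 1.645 × √(0.30 × 0.70/21)) / √(0.57 × 0.43/21)] = Φ[(0.27 − 0.1645)/0.1080] = Φ(0.977) = 83.6%. A two-sided 5% level in the same formula gives 75.3%.
- P(3 or fewer of 15 | 49%) = 2.12%.

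Neither is a calculation error.

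**2. The same power formula against 49%.** Φ[(0.08 − 1.645 × 0.1091)/0.1080] = Φ(−0.92) = 17.9% (10.8% two-sided).

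**3. Exact binomial.** The cut-off is the smallest response count whose upper-tail probability at the benchmark is no more than the one-sided level. The two-sided 95% interval corresponds to 2.5% in the upper tail.

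| n, rule | Cut-off vs 30% (power at 57%) | Cut-off vs 49% (power at 57%) | Counts that beat 30% but not 49% | Probability at a true 57% |
|---|---|---|---|---|
| 21, one-sided 5% | 11 (74.3%) | 15 (13.2%) | 11–14 | 74.3 − 13.2 = 61% |
| 21, two-sided 95% interval | 12 (58.6%) | 16 (5.7%) | 12–15 | 58.6 − 5.7 = 53% |
| 24, one-sided 5% | 12 (81.6%) | 17 (12.1%) | 12–16 | 69% |

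At the planned rate, 12 of 21 (57%) has an exact 95% interval of 34.0% to 78.2%, which excludes 30% and includes 49%.

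**4. The 2.1% statement at the other rate.** P(3 or fewer of 15 | 30%) = 29.7%.

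**5. Where 49% could come from.** The plan says nothing, so these are conjectures.

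- Mixed histology: (30 + 48 + 65.8)/3 = 47.9% with assumed equal weights. With half follicular and the rest split equally: 15 + 12 + 16.45 = 43%. Weighted by the cited study sizes (40, 63, 111): 54%.
- Independence combination of the two treatments: 1 − 0.70 × (11/15) = 48.7%.

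**6. The 6-response criterion does not settle the matter.** With 21 subjects it is met with probability 63.7% at a true 30% and 98.3% at a true 49%.

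**The case against.** The strongest defence is that the comparator is named. The power claim is tied to 30%, section 12.3.3 repeats it, and 49% enters only one conditional probability, which is correct as stated. No section tests the ORR against 49%. This stands: the 49% cut-offs above are a reader's comparison, not a planned analysis. It does not remove the problem, because sections 12.1 and 12.2.2 never say that the observed ORR will be judged against 30%, and the synopsis gives only 49%.

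A second defence is that the two figures can both be true. The 30% is one drug in one histology; the 49% is attached to a wider population with no treatment named. This also stands as a possibility, so a reader should not infer that the two rates are logically incompatible. If 49% does describe the mixed population, however, a follicular-only 30% is too low a null for the subjects enrolled.

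Three stronger readings are tempting and not supported:

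- That any phase 2 result would succeed against one rate and fail against the other. With 21 subjects and the one-sided rule, 10 or fewer fail against both and 15 or more succeed against both; at a true 57% the two rates agree about 39% of the time.
- That the power falls from 83.6% to 13%. That mixes methods. Like for like it is 83.6% to 17.9% by normal approximation, or 74.3% to 13.2% exact.
- That the plan contains an arithmetic mistake here. Both stated figures reproduce.

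**Conclusion.** The point holds as an inconsistent benchmark. The plan powers phase 2 against 30%, calls 49% historical without a source, and does not say which rate decides how the primary result is read. If the true ORR is the planned 57%, the chance that the reading depends on the choice is 61% with 21 subjects (exact one-sided 5%), 53% with an exact two-sided 95% interval, and 69% with 24 subjects (one-sided 5%). These sizes assume that 57% is the true rate and that the ORR would be compared with each benchmark by an exact binomial rule; the plan specifies neither test nor sidedness. The origin of 49% remains unknown.

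This should be fixed. It affects how the primary efficacy result is interpreted, but no planned test is invalidated.

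**What to change.** State one sourced benchmark that fits the enrolled histologies, or one per histology, and use it in the synopsis and in sections 12.1, 12.2.2 and 12.3.2. Say there that the observed ORR is judged against it, and by which test or interval.

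- **If the benchmark is 30%:** stop calling 49% historical, present it only as a hypothetical true rate, and add that three or fewer responses in 15 has probability 29.7% at 30%. Justify a follicular-only rate for a population that also includes mantle cell and marginal zone lymphoma.
- **If the benchmark is 49%:** give its source and restate the power at a true 57% with 21 subjects by one named method. That is 17.9% by the one-sided normal approximation that reproduces 83.6%, or 13.2% by the exact binomial, for which the figure against 30% is 74.3%.

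The cost is wording in the synopsis and section 12. A stated figure becomes less favourable on either branch. No subjects or procedures are added.
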